7. STATISTICAL METHODS

An SAP, providing details about the specific planned analyses and statistical tests, will be prepared and approved by the Sponsor and its designees prior to study database lock and unblinding of the single-blind subject treatment assignments.

For safety and immunogenicity endpoints, tests will be performed comparing each dose level to the placebo group. Additional tests may be performed between dose levels to determine dose response. All statistical tests will be performed at the 2-sided 5% level of significance. No adjustments for multiple testing will be considered. No imputations will be made for missing immunogenicity data.

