7.1. PLANNED ENROLLMENT AND REASON FOR SAMPLE SIZE

This is a Phase 1 study, where both descriptive and inferential statistical methods will be used to fully explore the preliminary data for planning of future studies and will define future study endpoints. This study is intended to provide initial safety, tolerability, and immunogenicity data for the vaccine candidate. In addition, immunogenicity endpoints will be evaluated for the potential of a dose-response relationship to increasing doses of the IP, including placebo as a 0-dose level.

The sample size for this Phase 1 study (N=36 subjects total: N=10 per vaccine dose level (30 vaccinees) and 6 placebo) was selected to provide initial data to obtain estimates of safety and immunogenicity parameters and their respective variabilities. Group size is based on prior experience with ERVEBO safety studies and assumptions from the responses seen in the preclinical studies. This Phase I study is therefore designed with the goal of providing further information for better planning of future in-human studies. As this is a FIH study of PHV01, no current human data exist to substantiate power or treatment effect estimates.

Safety: With a sample size of 10 subjects, an upper bound of 30.9% is established for the two-sided 95% confidence interval for the incidence of an AE in the case that the event is not observed according to the two-sided 95% (Clopper-Pearson) exact confidence interval.

Immunogenicity: Clinical data for the rVSV-ZEBOV-GP Ebola vaccine showed that a dose of 3x10⁶ pfu/mL yielded a day 29 GMT IgG ELISA titer of 1400 EU/mL and geometric standard deviation of 3.3. Assuming that the variability in responses to PHV01 is similar, the proposed group sizes afford 80% (alternate 90%) power to detect a 6.4-fold (alternate 8.6-fold) increase, comparing geometric mean ELISA titer using a two-sided test with alpha=0.05 for each vaccine group with the placebo group. Alternatively, performing the same comparison against placebo by pooling all three treatment groups with a total 30 vaccinated subjects, we would have 4.7-fold and an alternate 5.9-fold with 80% and 90% power, respectively.

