7.5.1. Analysis Addressing the Primary Study Objective (Safety)

Solicited symptoms occurring during the 28 days following vaccination will be summarized by treatment group and by relatedness. The incidence and severity of solicited AEs to the vaccine over the 28-day follow-up period will be calculated. Presentations will include the number and percentage of subjects with at least 1 local AE, and at least 1 general (systemic) AE, as well as the incidence of each AE individually.

The number of subjects with at least 1 incidence of an unsolicited AE reported up to 28 days after vaccination will also be summarized overall and by treatment group. The severity and temporal relationship of the unsolicited AEs to vaccination will also be assessed. Presentations will also summarize unsolicited AEs by grade and vaccine-relatedness. Serious AEs occurring at any point during the trial will be summarized and relatedness to vaccine will be assessed. The incidence rate of solicited AEs may be compared between each treatment group and placebo using Fisher's exact test and logistic regression.

The level of vaccinemia (on days 1 [at 0 and 6 hours], 2, 4, 8, 15, and 29) and shedding will be assessed on all subjects. The proportion of subjects with detected vaccinemia, as well as the geometric mean and AUC of vaccinemia level, will be presented at each time point where data are collected. The relationship between vaccinemia level and dose will be explored in a mixed model for repeated measures (MMRM) analysis that incorporates dose level, time, and other potential predictive factors. A similar model will be used to explore the relationship between dose and the AUC of the vaccinemia level.

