3. GENERAL STATISTICAL METHODS

3.1. Sample Size Justification

The sample size for this Phase 1 study (N=36 subjects; total N=10 per vaccine dose level [30 vaccinees and 6 placebo]) was selected to provide initial data and obtain estimates of safety and immunogenicity parameters and their respective variabilities. Group size is based on prior experience with ERVEBO safety studies and assumptions from the responses seen in the preclinical studies. This Phase I study is therefore designed with the goal of providing further information for better planning of future in-human studies. As this is a FIH study of PHV01, the sample size was established to provide reasonable information for descriptive purposes and not specifically designed for formal hypothesis testing.

Safety: With a sample size of 10 subjects, an upper bound of 30.9% is established for the 2-sided 95% confidence interval (CI) for the incidence of an AE in the case that the event is not observed according to the two-sided 95% (Clopper-Pearson) exact CI. Alternatively, when pooled together all 30 vaccinees, an upper bound of 11.6% is provided. This established the sample sizes needed to ensure minimal AE rates could be detected with confidence.

Immunogenicity: Clinical data for the rVSV-ZEBOV-GP Ebola vaccine showed that a dose of 3×10^6 pfu/mL yielded a Day 29 GMT IgG ELISA titer of 1400 EU/mL and geometric standard deviation (SD) of 3.3. Assuming that the variability in responses to PHV01 is similar, the proposed group sizes afford 80% (alternate 90%) power to detect a 6.4-fold (alternate 8.6-fold) increase, comparing geometric mean ELISA titer using a two-sided test with alpha=0.05 for each vaccine group with the placebo group. Alternatively, performing the same comparison against placebo by pooling all three treatment groups with a total 30 vaccinated subjects, we would have 4.7-fold and an alternate 5.9-fold with 80% and 90% power, respectively.

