3.2. General Methods

All data listings that contain or imply an evaluation date will contain a relative study day (Rel Day). Pre-treatment and on-treatment study days are numbered relative to the day of the first dose of study medication which is designated as Day 1. The preceding day is Day -1, the day before that is Day -2, etc. Post-treatment study days are numbered relative to the first dose and are designated as Day 1, Day 2, etc. for table and listing display. Data for time interval analysis and graphing will be displayed as days since dosing where Hour 6 timepoint on Day 1 is converted to 0.25 days.

All outputs will be incorporated into Microsoft Word or Excel files, or Adobe Acrobat PDF files, sorted and labeled according to the International Conference on Harmonisation (ICH) recommendations, and formatted to the appropriate page size(s).

Tabulations will be produced for appropriate demographic, baseline, immunogenicity, and safety parameters. For categorical variables, summary tabulations of the number and percentage of subjects within each category (with a category for missing data) of the parameter will be presented. For continuous immunogenicity variables, the number of subjects, geometric mean, median, geometric standard deviation (SD), minimum, and maximum values will be presented.

Other continuous variables (e.g., BMI) will be summarized by the number of subjects, mean, median, SD, minimum, and maximum values. Summarizations will be tabulated by treatment group.

Formal statistical hypothesis testing will be performed on the primary and secondary immunogenicity endpoints with all tests conducted at the 2-sided, 0.05 level of significance. Summary statistics will be presented, as well as CIs on selected parameters, as described in the sections below.

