- AESIs at baseline, and up to day 181 by SOC, PT and relatedness

The number and percentage of subjects with any AE type as described above will be summarized by treatment group and combined PHV01 group. Adverse events are summarized by subject incidence rates; therefore, in these tabulations, each subject will contribute once (i.e., the most related occurrence or the most intense occurrence) to each of the incidence rates in the analysis regardless of the number of episodes. Tabulation by relatedness to study vaccine will be categorized as Related (Definite, Probable, Possible) or Not related; while tabulation by severity will be graded as Grade 1 (Mild), Grade 2 (Moderate), Grade 3 (Severe), Grade 4 (Potentially life-threatening).

Additionally, a symptom score will also be used to summarize solicited local and systemic AEs. The symptom score is a scalar quantity that summarizes the overall severity of a subject's solicited AE experience. The symptom index for a given AE will be defined as individual unique toxicity grades reported for each TEAE multiplied by the duration of the TEAE. The individual symptom indices will then be summed for each subject to obtain their symptom score. Larger scores are indicative, overall, of more severe and/or AEs of longer duration; smaller scores are indicative, overall, of less severe and/or AEs of shorter duration.

If an AE is ongoing at the end of the observation period, the length of the observation period post vaccination will be used in the calculation of symptom index. If the severity is missing for any particular AE, then the corresponding symptom index will also be set to missing.

Symptom scores will be summarized descriptively by treatment group and the combined PHV01 treatment group. Symptom scores will be calculated separately for all solicited local and systemic AEs which started within 14 Days of vaccination. The mean, standard deviation, median, minimum, and maximum values will be tabulated.

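### For adverse-event incidence, the SAP specifies no confidence interval and no vaccine-minus-placebo estimate, and does not record that it drops the protocol's comparison with placebo

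*SAP*

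**What the plan says.** **Protocol.** Section 7 makes a general commitment: "For safety and immunogenicity endpoints, tests will be performed comparing each dose level to the placebo group". Section 7.5.1, which covers AEs specifically, is weaker: "The incidence rate of solicited AEs may be compared between each treatment group and placebo", by Fisher's exact test and logistic regression. Two of the seven primary safety endpoints in Protocol 3.1.1 mention active vaccination against placebo in a parenthesis.

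**SAP, scope of testing.** SAP 3.2 places testing elsewhere: "Formal statistical hypothesis testing will be performed on the primary and secondary immunogenicity endpoints". It promises CIs only for selected parameters named in later sections.

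**SAP, AE analysis.** SAP 4.4.2 reports AE incidence as follows: "The number and percentage of subjects with any AE type as described above will be summarized by treatment group and combined PHV01 group". No interval, difference or test is named. The section adds a symptom score (grade times duration), summarised by mean, SD, median and range. SAP 4.4.4 correlates the symptom index with viremia AUC. SAP 4.4.5 and 4.4.6 summarise laboratory values and vital signs.

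**SAP, sample size.** SAP 3.1 gives the zero-event upper limit of the two-sided 95% Clopper-Pearson interval as 30.9% for 10 subjects and adds that "when pooled together all 30 vaccinees, an upper bound of 11.6% is provided". It concludes: "This established the sample sizes needed to ensure minimal AE rates could be detected with confidence".

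**SAP, elsewhere.** SAP 4.3.2 specifies Clopper-Pearson intervals for seroconversion rates and Newcombe intervals for their differences.

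**The concern.** Three things do not fit together.

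1. The protocol's general statement commits to safety comparisons with placebo, its AE section makes them optional, and the SAP has none. SAP 1.1.1 says the SAP will outline differences from the protocol. SAP section 6 lists none and defers changes to the study report.
2. The exact interval that forms part of the rationale for n=10 and n=30 is not requested for any AE table. A zero count would be tabulated without the bound cited when the study was sized.
3. The same SAP specifies the interval methods needed, but applies them to seroconversion and seroresponse and not to AE incidence.

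The Day 29 interim analysis includes the AE tables by group and is meant to guide dose selection for the next trial (Protocol 7.2, SAP 3.12). Solicited symptoms also follow placebo: Protocol 1.5.1 quotes injection-site pain of 69.5% with the licensed rVSV Ebola vaccine against 12.8% with placebo. A reader choosing a dose needs the excess over placebo and its uncertainty. Percentages on denominators of 10 and 6 do not show that uncertainty.

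**Working it through.** **Inputs.** Group sizes: "N=10 per vaccine dose level (30 vaccinees) and 6 placebo" (Protocol 7.1). Rates for illustration, vaccine v placebo: pain 69.5% v 12.8%, swelling 16.5% v 3.0%, redness 11.9% v 1.5% (Protocol 1.5.1). Applying these Ebola-vaccine rates to PHV01 is an assumption.

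**Step 1: the plan's own figures.** With zero events the two-sided 95% Clopper-Pearson upper limit is 1 − 0.025^(1/n).

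- n=10: 30.85% (stated 30.9%; rounding only).
- n=30: 11.57% (stated 11.6%).
- n=6, placebo: 45.9% (not stated in the plan).

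The stated figures are right. The gap is that SAP 4.4.2 never asks for the interval.

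**Step 2: what the exact interval would show.** For one dose group, 1/10 gives 0.3% to 44.5%, 3/10 gives 6.7% to 65.2%, and 7/10 gives 34.8% to 93.3%.

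**Step 3: what a difference would show.** Newcombe's interval for d = p1 − p2, with Wilson limits (l, u) for each arm, runs from d − √[(p1−l1)² + (u2−p2)²] to d + √[(u1−p1)² + (p2−l2)²].

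For 7/10 v 1/6, the Wilson limits are 0.397 to 0.892 and 0.030 to 0.563, and d = 0.700 − 0.167 = 0.533.

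- Lower: 0.533 − √[0.303² + 0.397²] = 0.034.
- Upper: 0.533 + √[0.192² + 0.137²] = 0.769.

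| Counts, vaccine v placebo | Difference (points) | Newcombe 95% CI |
|---|---|---|
| 7/10 v 1/6 | +53 | 3 to 77 |
| 21/30 v 1/6 | +53 | 10 to 72 |
| 0/10 v 0/6 | 0 | −39 to +28 |

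**Step 4: would restoring the Fisher test help?** Two-sided power at 5%, by exact enumeration of all tables:

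| Event | 10 v 6 | 30 v 6 |
|---|---|---|
| Pain | 53% | 68% |
| Swelling | below 1% | below 1% |
| Redness | below 1% | below 1% |

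With 0/6 on placebo, p<0.05 needs at least 6/10 in one dose group (p=0.034) or 15/30 pooled (p=0.030). Tests would be weak even for the largest expected effect and nearly always silent for the others. Intervals are the more useful output.

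**Step 5: what the placebo group is.** Each dose is randomised in two blocks, 3:1 and 7:1 (SAP 1.2.2), so each dose has 1 + 1 = 2 concurrent placebo subjects, and 3 × 2 = 6 overall. A 10 v 6 contrast therefore uses four placebo subjects from the blocks of other doses. SAP 3.5 already pools placebo.

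**The case against.** The strongest reply is that descriptive safety reporting is a declared choice. SAP 3.1 says the trial was sized for description and not for formal testing, and a 36-subject first-in-human trial gains little from tests. That stands, and it is why the remedy asks for intervals and not p-values. It does not explain why the interval cited in SAP 3.1 is left out of the AE tables, nor why the protocol's commitment lapses unrecorded.

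Other parts of the reply also stand and limit the point. A reader might infer any of the following, and the documents do not support them:

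- *Safety yields only counts and percentages.* The symptom score, the viremia correlation and the laboratory and vital-sign summaries go further, although none is specified as a vaccine-placebo contrast. Safety is also one of two primary objectives.
- *Placebo is ignored.* It is a treatment group tabulated beside each dose.
- *The primary endpoints define a contrast.* The parenthesis reads at least as naturally as naming the groups for reporting.
- *The protocol promised a CI on AE incidence.* It did not; only the comparison with placebo differs. Because Protocol 7.5.1 says *may*, omitting the Fisher test is consistent with that section and conflicts only with section 7.
- *The omission is confined to AEs.* SAP 4.4.3 states no CI for viremia proportions either, although Protocol 7.5.2 promised one for vaccinemia.
- *Vaccine-attributable reactogenicity could not be stated.* Differences and exact intervals follow directly from the planned counts.
- *The exact CI alone set the sample size.* SAP 3.1 also cites prior experience with the licensed Ebola vaccine and preclinical responses.

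**Conclusion.** The point holds in a limited form. For AE incidence, SAP 4.4.2 specifies n (%) by group with no confidence interval and no vaccine-minus-placebo estimate. This departs, without a record in the SAP, from Protocol section 7, which itself conflicts with Protocol 7.5.1. It also leaves uncomputed an interval on which SAP 3.1 partly rests the group sizes.

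Nothing in the plan is miscalculated, and the cohort safety reviews and pausing rules are untouched. What is at stake is how precisely a primary safety endpoint is presented when it feeds the Day 29 dose-selection analysis. The unstated uncertainty is large: a 53-point difference at 10 v 6 carries an interval of 3 to 77 points, and 0/6 on placebo does not exclude a rate of 45%.

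The event counts are illustrative and the power figures assume the Ebola-vaccine rates. The exact zero-event bounds depend only on the group sizes. The change is worth making because it is cheap, but it is not a condition for the trial to be valid.

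**What to change.** 1. In SAP 4.4.2, add a Clopper-Pearson 95% CI to AE incidence for each dose, combined PHV01 and pooled placebo.
2. Add the risk difference from pooled placebo, with the Newcombe 95% CI already used in SAP 4.3.2, for each dose and combined PHV01. Limit this to any solicited local AE, any solicited systemic AE, any Grade 3 or higher AE, any related AE, and individual solicited terms over the main solicitation window (through Day 15). Label them as descriptive estimates with no significance claim.
3. State that the comparator pools placebo subjects across sequential cohorts, with only two randomised within each dose's own blocks.
4. Reconcile Protocol section 7, Protocol 7.5.1 and SAP 3.2 on whether safety endpoints are tested, and record the change in the SAP.

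**Cost.** The methods are already specified for seroconversion, so the work is wording and table output. That output is not trivial: SAP 4.4.2 lists 30 solicited CRF terms, and four contrasts each gives 30 × 4 = 120 intervals, plus 4 × 4 = 16 for the composites. They will be wide and unadjusted for multiplicity, so an isolated interval excluding zero should not be read as a finding.

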6.5. SEVERITY ASSESSMENT

All AEs will be assessed for severity by the Investigator. Inherent in this assessment is the medical and clinical consideration of all information surrounding the event, including any medical intervention required. Each event will be assigned one of the following categories: mild, moderate, severe, or life-threatening. Refer to the grading scale in APPENDIX 1 for further guidance in the assignment of severity. Any Grade 4 (life-threatening) AE must be reported as an SAE.

The eCRF for AEs will reflect only the highest severity for continuous days an event occurred. The following criteria below may be used for any symptom not included in the grading scale:

Mild (Grade 1): Does not interfere with routine activities; minimal level of discomfort.

Moderate (Grade 2): Interferes with routine activities; moderate level of discomfort.

Severe (Grade 3): Unable to perform routine activities; significant level of discomfort.

Potentially life-threatening (Grade 4): Hospitalization or ER visit for potentially life-threatening event.

The FDA guidelines for toxicity will be followed; however, if a subject is evaluated in an emergency room for nonlife threatening illness or symptoms (i.e., visits emergency department on weekend for mild problems because the physician's office is closed), the information from that visit will be reviewed and severity of the AE will be assessed according to the subject's clinical signs and symptoms.

As defined by the ICH guideline for GCP, the term "severe" is often used to describe intensity (severity) of a specific event (as in mild, moderate, or severe myocardial infarction); the event itself, however, may be of relatively minor medical significance (such as severe headache). This is **not** the same as "serious", which is based on subject/event **outcome** or **action** criteria usually associated with events that pose a threat to a subject's life or functioning. Seriousness (not severity) serves as a guide for defining regulatory reporting obligations.

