4.4.2. Adverse Events

AEs will be assessed by evaluating reactogenicity (local reactions and systemic reactions) and the occurrence of post-vaccination solicited local reactions and systemic AEs through day 15. Solicited AEs for days 16-29 are limited to instances of neurological signs and symptoms, arthritis, and rash. Arthritis, rash, and neurologic events should be evaluated throughout the study and may include expert consultation.

All AEs (including solicited AEs) will be coded using the MedDRA coding system and displayed in tables and data listings using system organ class (SOC) and preferred term (PT). Note that solicited and unsolicited AEs will be analyzed and presented separately. The severity of all AEs will be graded in accordance with the FDA document "Guidance for Industry: Toxicity Grading Scale for Healthy Adult and Adolescent Volunteers Enrolled in Preventive Vaccine Clinical Trials" described in Section 5.

Analyses of AEs will be performed for those events that are considered treatment-emergent, where treatment-emergent is defined per protocol as any AE with onset after the administration of study medication.

All AEs occurring on-study will be listed in subject data listings.

By-subject listings also will be provided for the following: subject deaths, SAEs, AEs leading to withdrawal, solicited local site AEs, solicited systemic AEs, MAAEs, and AESIs.

Solicited AEs are predefined local events at the injection site and systemic events for which the subject is specifically questioned and facilitated by use of memory aides.

The following local AEs will be solicited:

- Arm Pain [CRF term: Pain at Site of Injection]
- Local Tenderness [CRF term: Tenderness at Site of Injection]
- Erythema (Redness) [CRF term: Redness at Site of Injection]
- Induration (Swelling/Firmness) [CRF term: Swelling at Site of Injection]

Note: CRF term in the square brackets refers to the term used on the Adverse Event Case Report Form to capture the local solicited AEs.

The following systemic (non-injection site) AEs will be solicited:

- Subjective Fever [CRF term: Subjective Fever]
- Objective Fever [CRF term: Fever]
- Chills [CRF term: Chills]
- Sweats [CRF term: Sweats]
- Myalgia [CRF term: Myalgia]
- Arthralgia [CRF term: Arthralgia]
- Joint Swelling [CRF term: Joint Swelling]
- Joint Tenderness [CRF term: Joint Tenderness]
- Fatigue [CRF term: Fatigue]

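### The symptom score gives an ongoing AE the whole time since vaccination as its duration, which inflates its index by grade × (onset day − 1)

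*SAP*

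**What the plan says.** SAP Section 4.4.2 defines the symptom index for an AE as "individual unique toxicity grades reported for each TEAE multiplied by the duration of the TEAE". It then says "The individual symptom indices will then be summed for each subject to obtain their symptom score", and gives the intended reading: "Larger scores are indicative, overall, of more severe and/or AEs of longer duration".

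For events that have not ended, the next paragraph substitutes another quantity for the duration: "If an AE is ongoing at the end of the observation period, the length of the observation period post vaccination will be used".

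The scope is set by "Symptom scores will be calculated separately for all solicited local and systemic AEs which started within 14 Days of vaccination", and the group summary by "The mean, standard deviation, median, minimum, and maximum values will be tabulated".

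The end of the observation period is not defined for the score. Section 4.4.2 describes general solicitation as covering "the occurrence of post-vaccination solicited local reactions and systemic AEs through day 15". It also tabulates neurological, joint and skin terms up to Day 181. Section 4.4.4 uses the index again, in Spearman correlations with viremia AUC, for solicited AEs from Day 0 to Day 29.

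**The concern.** The substitution contradicts the definition that precedes it. Two subjects with an AE of the same grade, one starting on Day 1 and the other on Day 14, both unresolved, receive the same index although one was observed with the event for far longer. An event that began late is credited with days on which it did not exist.

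Second-week events are plausible here. For the related licensed vaccine, Protocol Section 1.5.1 reports arthritis in 19 of 418 vaccinees (median onset 12 days, median duration 8 days) and dermatitis in 24 of 418 (median onset 9 days, median duration 7 days). An event with those arthritis medians would begin inside the 14-day onset limit and run to about day 12 + 8 = 20, so it would be unresolved at a Day 15 cut-off.

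At stake are the group mean, SD and maximum of the score, and subjects' ranks in the correlation with viremia AUC.

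**Working it through.** The documents give no numerical value for the score, so there is no figure to reproduce. The check is direct arithmetic.

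**Inputs.** Day 1 is the day of dosing (SAP 3.2). Group sizes are 10 per dose level and 6 placebo (SAP 3.1). The end day *E* is an assumption, taken as 15, 29 or 181 because each appears as an AE window in the SAP. Inclusive day counting is also an assumption.

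**Formulas**, for grade *g* and onset day *s*:

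- Rule as written: *g* × *E*
- Counted from onset: *g* × (*E* − *s* + 1)
- Excess: *g* × (*s* − 1), which does not depend on *E*

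**Grade 2 AE, onset Day 13, unresolved:**

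| End of period | As written | From onset | Excess | Ratio |
|---|---|---|---|---|
| Day 15 | 2 × 15 = 30 | 2 × 3 = 6 | 24 | 5.0 |
| Day 29 | 2 × 29 = 58 | 2 × 17 = 34 | 24 | 1.7 |
| Day 181 | 2 × 181 = 362 | 2 × 169 = 338 | 24 | 1.07 |

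The effect on a dose-group mean is 24 / 10 = 2.4 points. Without inclusive counting the Day 15 row is 2 × 14 = 28 against 2 × 2 = 4, and the excess is still 24.

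**Ranking.** A Grade 1 AE starting on Day 14 and unresolved at Day 15 scores 1 × 15 = 15 as written and 1 × 2 = 2 from onset. A resolved Grade 3 AE of four days scores 3 × 4 = 12. The rule puts the two-day mild event above the four-day severe one.

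**Effect on a group of 10, Day 15 end.** One subject has that Grade 1 event. The other nine are each given the same score, which is an assumption:

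| Score of each other subject | Mean, as written | Mean, from onset | Event's share of total, as written | Event's share, from onset |
|---|---|---|---|---|
| 1 | 24/10 = 2.4 | 11/10 = 1.1 | 15/24 = 62.5% | 2/11 = 18% |
| 4 | 51/10 = 5.1 | 38/10 = 3.8 | 15/51 = 29% | 2/38 = 5% |
| 10 | 105/10 = 10.5 | 92/10 = 9.2 | 15/105 = 14% | 2/92 = 2% |

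In the first row the SD is 4.43 instead of 0.32. The median is unchanged in all three rows.

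**The case against.** The strongest reply is that little depends on this score. It is not among the primary or secondary endpoints, no between-group test of it is planned, and the safety conclusions rest on incidence and severity tables and by-subject listings. Few events should be affected: at the related vaccine's rates, a group of 10 would expect 10 × 19/418 = 0.45 arthritis cases and 10 × 24/418 = 0.57 dermatitis cases. Protocol Sections 5.4.1 and 5.4.2 follow such events to resolution, so most will have an end date well before Day 181. Spearman's coefficient responds only if a rank changes. All of this stands, and it limits the importance. It does not make the rule agree with the index definition.

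Three stronger readings are tempting, and the documents do not support them.

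- A reader might set 362 (Day 181 end) against 6 (Day 15 end) and blame the rule for the whole gap. Those values belong to different windows. Within one window the excess is 24; the rest comes from the length of the period, which is a separate gap in the definition.
- A reader might infer that one late mild event will dominate a dose group. The second table shows that this needs very low scores in everyone else.
- A reader might see a conflict between the index formula and Protocol Section 6.5, which states: "The eCRF for AEs will reflect only the highest severity for continuous days an event occurred". If each AE record carries one grade, the two agree. Highest grade times duration is then a choice of index, not a demonstrated error.

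**Conclusion.** The rule is wrong as written, and no other part of either document corrects it. It adds grade × (onset day − 1) to the index of every unresolved AE. For the scores in SAP 4.4.2 the 14-day onset limit caps this at about 14 points per grade level (onset Day 15: 15 − 1 = 14), or about 1.4 points per grade on the mean of a 10-subject group. In relative terms the distortion is large for a Day 15 end and small for a Day 181 end.

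The mean, SD and maximum are affected, the median little or not at all. Subject ranks can change in the AUC correlation within dose groups of 10. The size of the excess rests on the literal reading that the period runs from vaccination. It does not depend on the end day or on the day-count convention, provided the same convention is used on both sides. How far a group's summary moves depends on the assumed scores of the other subjects. This is a correction to a descriptive safety summary and does not threaten the trial's main safety conclusions.

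**What to change.** In SAP Section 4.4.2, set the duration of an AE that is ongoing at the end of the observation period to (last day of the observation period − onset day + 1), and state that days are counted inclusively.

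State the last day of the period for each use of the index: for example, Day 15 for the symptom scores in 4.4.2 and Day 29 for the Day 0–29 AUC correlation in 4.4.4. A single Day 15 cut-off for both would break the match with the AUC window in 4.4.4 and would truncate joint and skin events that are solicited through Day 29.

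The cost is a few lines of SAP text and one changed derivation. Onset dates are already collected, and SAP Section 3.10 already covers partial or missing ones, so trial conduct and data collection do not change.
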